## **6 STUDY PERIODS, TREATMENT REGIMENS AND POPULATIONS FOR ANALYSES**

### **6.1 Study Periods**

- Baseline period:
  - Baseline evaluations or pre-treatment events will be defined as evaluations or events that occur before the date and time of the first dose of study treatment. Evaluations (laboratory tests, pulse oximetry, vital signs) on the same date and time of the first dose of study treatment will be considered as baseline evaluations. Events (AEs) on the same date and time of the first dose of study treatment will not be considered as pre-treatment events.
  - In cases where the time (onset time of event or evaluation time and dosing time) is missing or not collected, the following definitions will apply:
    - ◆ Pre-treatment AEs will be defined as AEs with an onset date prior to but not including the day of the first dose of study treatment;
    - ◆ Baseline evaluations (laboratory tests, pulse oximetry, vital signs) will be defined as evaluations with a date (and time if collected) on or prior to the date of first dose of study treatment.
  - If there are multiple valid observations in the baseline period, then the latest non missing observation will be used as the baseline in the analyses. If multiple observations exist on the latest collection date (and time if collected), the record with the latest data entry date and time will be used. If multiple observations exist on the latest collection date (and time if collected) and data entry date and time, then the first observation is used as baseline, unless otherwise specified.
- For nivolumab Anti-Drug Antibody (ADA), the baseline record of IDO1 inhibitor immunogenicity (IMG) evaluation must be less than the date and time of the first Nivolumab/IDO1 inhibitor dose date and time.
- Post baseline period:
  - On-treatment AEs will be defined as AEs with an onset date and time on or after the date and time of the first dose of study treatment (or with an onset date on or after the day of first dose of study treatment if time is not collected or is missing). For subjects who are off study treatment, AEs will be included if event occurred within a safety window of 100 days after the last dose of study treatment if a participant received BMS-986205 + NIVO (or 30 days after the last dose of study treatment if a participant received only BMS-986205). No “subtracting rule” will be applied when an AE occurs both pre-treatment and post-treatment with the same preferred term and grade.
  - On-treatment evaluations (laboratory tests, pulse oximetry and vital signs) will be defined as evaluations taken after the day (and time, if collected and not missing) of first dose of study treatment. For subjects who are off study treatment, evaluations should be within a safety window of 100 days after the last dose of study treatment if a participant received BMS-986205 + NIVO (or 30 days after the last dose of study treatment if a participant received only BMS-986205).

- Post baseline period by phase:
  - Mono lead-in period starts with the first dose of BMS986205 and end prior to first dose of nivolumab.
    - ◆ Mono lead-in AEs will be defined as AEs with an onset date and time on or after the date and time of the first dose of initial mono study treatment (or with an onset date on or after the day of first dose of initial mono study treatment if time is not collected or is missing) and prior to the date-time of the first dose of nivolumab (or with an onset date prior to the day of first dose of nivolumab if time is not collected or is missing). For subjects who discontinue during Mono lead in, AEs will be included if event occurred within a safety window of 30 days after the last dose of BMS-986205 initial mono study treatment. No “subtracting rule” will be applied when an AE occurs both pre-treatment and post-treatment with the same preferred term and grade.
    - ◆ Mono lead-in evaluations (laboratory tests, pulse oximetry and vital signs) will be defined as evaluations taken after the day and time of the first dose of initial mono study treatment (or with a start date after the day of first dose of initial mono study treatment if time is not collected or is missing) and prior to the date-time of the first dose of nivolumab (or with a start date on or prior to the day of first dose of nivolumab if time is not collected or is missing). For subjects who discontinue during Mono lead in, evaluations will be included if evaluation is taken within a safety window of 30 days after the last dose of BMS-986205 initial mono study treatment.
  - Combination Treatment Period starts with the first dose date-time of initial nivolumab.
    - ◆ Combination treatment AEs will be defined as AEs with an onset date and time on or after the date and time of the first dose of nivolumab (or with an onset date on or after the day of first dose of nivolumab if time is not collected or is missing). For subjects who are off study treatment, AEs will be included if event occurred within a safety window of 100 days after the last dose of study treatment.
    - ◆ Combination treatment evaluations (laboratory tests, pulse oximetry and vital signs) will be defined as evaluations taken after the day (and time, if collected and not missing) of first dose of nivolumab. For subjects who are off treatment, evaluations will be included if evaluation is taken within 100 days of the last dose of study medication.

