Study Day of Sample Collection	Event	Time (Relative To BMS-986205 Dose) Hour: Min	BMS-986205 [REDACTED] Plasma Sample	BMS-986205 [REDACTED] Urine Sample	Nivolumab Serum Sample	Nivolumab ADA Sample
Cycle 0						
C0D1		1:00	X	X 0-8 h		
		2:00	X			
		3:00	X			
		4:00	X			
		6:00	X			
		8:00	X			
C0D2	predose	0:00	X	X 8-24 h		
C0D8	predose	0:00	X			
C0D14	predose	0:00	X			
		1:00	X			
		2:00	X			
		3:00	X			
		4:00	X			
		6:00	X			
		8:00	X			
C0D15 ^a	predose		X			
Cycle 1						
C1D1	predose ^b	0:00	X		X	X
	EOI ^c	1:00	X		X	
		2:00	X			
		3:00	X			
		4:00	X			
		6:00	X			
		8:00	X			
C1D2	predose		X			

Table 9.5.2-1: Pharmacokinetic, Anti-Drug Antibody (ADA) for BMS-986205 and Nivolumab

Study Day of Sample Collection	Event	Time (Relative To BMS-986205 Dose) Hour: Min	BMS-986205 [REDACTED] Plasma Sample	BMS-986205 [REDACTED] Urine Sample	Nivolumab Serum Sample	Nivolumab ADA Sample
Cycle 3						
C3D1	predose	0:00	X		X	X
	EOI	1:00	X		X	
		2:30 – 4:00	X			
Cycle 5 +						
Every 4 Cycles from C5D1	predose	0:00	X		X	X
	EOI	1:00	X		X	
EOT and FU						
EOT			X		X	X
FU-1			X		X	X
FU-2			X		X	X

^a This sample should be taken 24 hours after the previous BMS-986205 dose on Cycle 0 Day 14 if Cycle 1 Day 1 does not occur on the next day of Cycle 0 Day 14.

^b This sample should be taken 24 hours after the previous BMS-986205 dose on Cycle 0 Day 14 if Cycle 1 Day 1 occurs on the next day of Cycle 0 Day 14.

^c EOI samples should be taken immediately prior to stopping the nivolumab infusion (preferably within 2 minutes prior to the end of infusion). If the end of infusion is delayed to beyond the nominal infusion duration, the collection of this sample should also be delayed accordingly.

[figure not shown]
The plasma and urine samples of BMS-986205 [REDACTED] will be analyzed by validated [REDACTED] liquid chromatography-mass spectrometry (LC-MS) assays as applicable, and serum samples of nivolumab and anti-nivolumab antibody will be analyzed by validated immunoassays. In addition, plasma samples will be archived for potential additional metabolite analysis, if the need arises and to the extent possible. Treatment assignments will be released to the bioanalytical laboratory in order to minimize unnecessary analysis of samples.

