## **2 STUDY DESCRIPTION**

### **2.1 Study Design**

This is a Phase 1/2, open-label study of BMS-986205 administered as a monotherapy and in combination with nivolumab in participants with advanced malignant solid tumors.

Treatment will start with a 2-week monotherapy lead-in (Cycle 0) whereby BMS-986205 100 mg oral daily dose must be administered with a meal at approximately the same time each day.

Participants will then proceed to receive the combination of nivolumab and BMS-986205. Nivolumab will be administered at a dose of 480 mg IV Q4W.

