## 6.3 Populations for Analyses

- Enrolled subjects Population: All subjects who signed the informed consent form and obtained a subject number.
- Treated subjects Population: All enrolled subjects who received at least one dose of any study treatment.
- Pharmacokinetic Population: All enrolled subjects who received at least one dose of any study treatment and have any available concentration-time data.
- Evaluable Pharmacokinetic Population: A subset of the PK Population, defined as all subjects who have adequate PK profiles or have at least one evaluable PK parameter. All available derived PK parameter values will be included in the PK data set and reported, but only participants with evaluable PK will be included in the summary statistics.
- Immunogenicity Population: All enrolled subjects who received at least one dose of nivolumab and have a baseline and at least one post-treatment immunogenicity measurement.

Unless otherwise specified, the safety analyses will include all treated subjects.

Unless otherwise specified, the efficacy analyses will include all treated subjects.

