### 7.4.2 Modifications of Study Therapy

#### 7.4.2.1 Dose Delays

Each BMS-986205 and nivolumab may be delayed.

A dose of nivolumab will be considered as actually delayed if the delay is exceeding 3 days (i.e. greater than or equal to 4 days from scheduled dosing date) for nivolumab/IDO1 inhibitor.

BMS-986205 is administered as a tablet daily. A dose of BMS-986205 will be considered as actually delayed (interrupted) if BMS-986205 was not administrated for at least 1 day. Interruption means the continuous oral dosing was stopped or held for a period of time prior to resuming.

All study drugs must be delayed until treatment can resume. Reason for dose delay will be retrieved from CRF dosing pages.

The following parameters will be summarized by study drug:

- Number of subjects with at least one dose delayed, the number of dose delays per subject, the reason for dose delay and the length of dose delay.

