#### **7.4.2.4 *Dose Reductions***

Dose reductions (within subject) are not permitted for nivolumab/IDO1 inhibitor.

Number of subjects with at least one dose reduction, the reason for dose reduction, and the number of dose reductions per subject will be summarized for BMS-986205 only.

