## **7.7 Pharmacokinetics**

The BMS-986205 and nivolumab concentration data obtained in this study will also be combined with data from other studies in the clinical development program to develop a population PK

model. This model will be used to evaluate the effects of intrinsic and extrinsic covariates on the PK of BMS-986205 and nivolumab/IDO1 inhibitor. In addition, exposure-response analyses with selected efficacy and safety endpoints may be conducted. Results of population PK and exposure response-analyses will be reported separately.

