### Sample ADA Status:

- Baseline ADA-positive sample: ADA is detected in the last sample before initiation of treatment
- Baseline ADA-negative sample: ADA is not detected in the last sample before initiation of treatment
- ADA-positive sample: After initiation of treatment, (1) an ADA detected (positive seroconversion) sample in a subject for whom ADA is not detected at baseline, or (2) an ADA detected sample with ADA titer to be at least 4-fold or greater ( $\geq$ ) than baseline positive titer
- ADA-negative sample: After initiation of treatment, ADA not positive sample relative to baseline

Next, using the sample ADA status, subject ADA status is defined as follows:

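### Does the loose wording of the nivolumab ADA baseline in SAP 6.1 and Appendix 2 leave participants without a baseline sample?

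*SAP*

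**What the plan says.** SAP 6.1 sets a general baseline at the first dose of study treatment, then adds a separate bullet for nivolumab ADA. That bullet describes the record as an immunogenicity evaluation of the IDO1 inhibitor and requires that it "must be less than the date and time of the first Nivolumab/IDO1 inhibitor dose date and time".

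SAP Appendix 2 classifies samples without naming a drug. A baseline-positive sample is one where "ADA is detected in the last sample before initiation of treatment". A later sample is positive if ADA appears where there was none at baseline, or if the titre reaches at least 4 times the baseline titre.

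SAP 6.3 limits the immunogenicity population to nivolumab recipients who "have a baseline and at least one post-treatment immunogenicity measurement". Protocol 10.2 sets the same limits. The population paragraph of Appendix 2 speaks of all treated subjects, but also asks for a baseline and a post-baseline assessment.

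In Protocol Table 9.5.2-1 the ADA column is blank throughout Cycle 0. The first entry is Cycle 1 Day 1 (C1D1) predose.

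**The concern.** BMS-986205 is the IDO1 inhibitor in this trial, so the slash label in SAP 6.1 can be taken to mean whichever of the two drugs is given first. SAP 2.1 has treatment opening with two weeks of BMS-986205 alone, so the Appendix 2 wording, taken literally, also points to Cycle 0 Day 1 (C0D1). No ADA sample is planned before that dose.

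On that reading nobody has a baseline, and both population definitions require one. The incidence of ADA to nivolumab is a stated secondary endpoint, and seroconversion and the 4-fold rise both need a baseline value. The C1D1 predose sample, taken before any nivolumab, would even count as a post-treatment sample. An endpoint that is either usable or empty depending on how two loosely worded sentences are programmed deserves a check.

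**Working it through.** The plan gives no ADA figure to reproduce. The check counts scheduled samples before each possible anchor and then asks which anchor the text supports.

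**Inputs**
- ADA draws over 12 cycles (Protocol Table 9.5.2-1): C1D1, C3D1, C5D1 and C9D1 predose, end of treatment, and the first two follow-up visits. That is 4 + 1 + 2 = 7.
- Predose samples fall 0 to 30 minutes before BMS-986205 (Protocol 9.5.2).
- Nivolumab starts about 30 minutes after BMS-986205 (Protocol 7.1.2).
- C1D1 comes at the earliest 14 days after C0D1, which is 14 × 24 = 336 hours.

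**Timing of the first ADA sample**
- Relative to the first nivolumab infusion: (0 to 30) + 30 = 30 to 60 minutes before.
- Relative to the first BMS-986205 dose: at the earliest 336 − 0.5 = 335.5 hours after.

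| Anchor | Draws strictly before it | Baseline sample |
|---|---|---|
| First BMS-986205 dose, C0D1 | 0 of 7 | none |
| BMS-986205 dose on C1D1 (first combination day) | 1 of 7 | C1D1 predose |
| First nivolumab dose, C1D1 | 1 of 7 | C1D1 predose |

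The last two rows select the same sample, even under the strict inequality in SAP 6.1. Only the first row differs, and it yields nothing.

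**Which anchor the text supports**
1. The slash label recurs in the SAP. In 7.4.2.1 the delay rule for nivolumab ends "greater than or equal to 4 days from scheduled dosing date) for nivolumab/IDO1 inhibitor", and BMS-986205 then gets its own rule of one missed day. In 7.4.2.4, "Dose reductions (within subject) are not permitted for nivolumab/IDO1 inhibitor" is followed at once by a summary of BMS-986205 reductions, which Protocol 7.4.1 allows (one step, 100 mg to 50 mg) while allowing none for nivolumab. In 7.7 the covariate model concerns effects "on the PK of BMS-986205 and nivolumab/IDO1 inhibitor", listed as separate items. In all three places the label means nivolumab.
2. The 6.1 bullet opens by naming nivolumab ADA and stands apart from the general baseline rule. Anchored at C0D1 it would add little beyond refusing a sample timed exactly at the dose.
3. Appendix 2 defines status for antibodies to nivolumab, the only ADA assayed. The treatment whose start matters for those antibodies is nivolumab. Exclusion criterion 3b in Protocol 6.2 bars earlier anti-PD-1 and anti-PD-L1 therapy, so C1D1 predose is a true pre-exposure sample.
4. Protocol 9.5.2 collects ADA samples from participants on combination treatment. Someone who stops in the lead-in lacks the required samples, so the broader population phrase in Appendix 2 selects the same people as 6.3.
5. SAP 6.1 already uses the first nivolumab date and time to open the combination period, so the variable an analyst needs exists.

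**The case for a change.** The strongest case for a change is that an SAP should fix a derivation and not leave it to inference. The 6.1 bullet names an assay that does not exist in this study, its label is undefined, and Appendix 2 names no drug in any of the seven places where it or SAP 7.6.14 refers to the start of treatment (4 for sample status, 2 for subject status, 1 in 7.6.14). One literal reading empties the evaluable set of a secondary endpoint, and a few words would settle it without touching sampling.

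The wording faults stand. They are in the text and are not products of redaction or PDF extraction. The consequence does not stand. No two usable readings give different baselines, so no choice between them can shift ADA incidence or the titre comparison. The two rules conflict only if they are given different anchors, and nothing in the SAP does that; linking the design narrative in 2.1 to the Appendix 2 phrase is an inference. If someone did program C0D1, the result would be an empty table, visible on the first run. That is unlike a hidden bias, which could pass into a report unnoticed.

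**Conclusion.** This is a clerical slip and a small gap that analysts will fill correctly. The baseline is the last sample before the first nivolumab dose: one scheduled sample per participant, C1D1 predose. Writing that down would change the baseline of no participant and the ADA status of none, compared with the definition the context already gives. The endpoint is descriptive, in about 12 participants, and Appendix 2 keeps every available ADA sample in the dataset and listing whatever the subject-level classification.

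The conclusion assumes that the C1D1 predose sample is drawn on schedule and that sample and dose times are recorded, so that the strict ordering on that day can be verified. A participant who missed the draw would lack a baseline under every reading, which is a missing-data matter and not a fault of the definition.

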Participants who discontinue the treatment phase will enter the Clinical/Safety Follow-Up period. Participants must be followed for at least 100 days after the last dose of study therapy or 30 days if participant only received BMS-986205. Follow-up visits should occur at Days 30, 60, and 100 (\pm 10 days) after the last dose of study therapy or should coincide with the date of discontinuation (\pm 10 days) if date of discontinuation is greater than 30 days after the last dose of study therapy to monitor for AEs. All participants will be required to complete one (if participant only received BMS-986205) or three Clinical/Safety Follow-Up visits regardless of whether they start a new anti-cancer therapy, except those participants who withdraw consent for study participation.

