#### Clinical/Safety Follow-Up

Upon completion of 48 weeks of combination treatment (or up to a maximum of 96 weeks if applicable), all participants will enter the Clinical/Safety Follow-Up period after the decision is made to discontinue the participant from treatment (eg, at end of treatment [EOT]).

For participants who complete all scheduled cycles of therapy, the EOT visit will be the same as the last scheduled and completed on-treatment visit, and the start of the Week 1 Clinical/Safety Follow-Up visit. For participants who do not complete all scheduled cycles of therapy, the EOT visit will be the most recent on-treatment visit (with all available safety and response data) and does not need to be repeated, and will be considered the start of the Week 1 Clinical/Safety Follow-Up visit.

Participants who discontinue the treatment phase will enter the Clinical/Safety Follow-Up period. Participants must be followed for at least 100 days after the last dose of study therapy or 30 days if participant only received BMS-986205. Follow-up visits should occur at Days 30, 60, and 100 ( $\pm$  10 days) after the last dose of study therapy or should coincide with the date of discontinuation ( $\pm$  10 days) if date of discontinuation is greater than 30 days after the last dose of study therapy to monitor for AEs. All participants will be required to complete one (if participant only received BMS-986205) or three Clinical/Safety Follow-Up visits regardless of whether they start a new anti-cancer therapy, except those participants who withdraw consent for study participation.

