## **4.1 Efficacy Endpoints**

### **4.1.1 Objective Response Rate**

Objective Response Rate (ORR) is defined as the number of treated subjects who achieve a best response of confirmed complete response (CR) or confirmed partial response (PR) based on investigator assessments (using RECIST v1.1 criteria) divided by the number of all treated subjects.

Best Overall Response (BOR) is defined as the best response, as determined by the investigator, recorded between the date of first dose and the date of objectively documented progression per RECIST v1.1 criteria or the date of subsequent therapy (including tumor-directed radiotherapy and tumor-directed surgery), whichever occurs first. For subjects without documented progression or subsequent therapy, all available response designations will contribute to the BOR determination. Confirmation of response is required at least 4 weeks after the initial response.

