#### **7.1.2 *Laboratory Tests***

Clinical laboratory parameters (hematology, serum chemistry and electrolytes) will be evaluated.

Laboratory tests will be graded using the NCI Common Terminology Criteria, and the most recent version of the criteria at the time of the database lock will be used.

Clinical laboratory data will be first analyzed using International System of Units (SI).

Analyses will be repeated using US conventional units.

In the laboratory summary tables, unless otherwise specified, subjects will be counted only once for each lab parameter according to their worst on treatment CTC grade (worst being the highest CTC grade). The laboratory tables and listings will be sorted by laboratory category, laboratory subcategory and laboratory test code sequence number.

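### SAP 6.1 does not cut the post-treatment safety window at subsequent anti-cancer therapy, so laboratory and all-causality event tables can include effects of the next regimen

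*SAP*

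**What the plan says.** **The window.** SAP 6.1 defines on-treatment adverse events by days since the last dose: "For subjects who are off study treatment, AEs will be included if event occurred within a safety window of 100 days after the last dose" when the combination was given, and 30 days when only BMS-986205 was given. Laboratory tests, pulse oximetry and vital signs follow suit: "For subjects who are off study treatment, evaluations should be within a safety window of 100 days after the last dose of study treatment", again with 30 days for BMS-986205 alone. For the combination phase, "evaluations will be included if evaluation is taken within 100 days of the last dose of study medication". None of these definitions mentions another anti-cancer therapy.

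**Follow-up.** Protocol 5.1 requires the follow-up visits "regardless of whether they start a new anti-cancer therapy", and SAP 2.1 repeats this. Protocol Table 2-4 schedules chemistry, CBC and LFTs at Days 30, 60 and 100 (±10 days). Protocol 7.7.1 lifts the ban on other anti-cancer therapy for participants in follow-up.

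**The tables.** Under SAP 7.1.2 each participant is counted once per laboratory parameter, "according to their worst on treatment CTC grade". SAP 7.6.10.1 to 7.6.10.3 build the shift tables from the same value, and the hepatic counts in 7.6.10.5 also use on-treatment evaluations. SAP 7.1.1 makes the AE tables all-causality by default and treats a missing relationship as related. Separate drug-related tables are planned in 7.6.2 to 7.6.6. SAP 7.6 tabulates safety by phase and overall.

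**Efficacy, by contrast.** Best overall response is taken up to documented progression "or the date of subsequent therapy (including tumor-directed radiotherapy and tumor-directed surgery), whichever occurs first" (SAP 4.1.1). SAP 4.1.2 censors duration of response at the last evaluable assessment before subsequent therapy. New therapies are recorded (Protocol Table 2-4), but outside efficacy the SAP only lists them (7.4.3.2).

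**The concern.** A participant who stops for progression may start another treatment well inside 100 days. Blood counts and liver tests taken on that treatment would then enter the combination-phase tables. Laboratory values carry no causality assessment, so a single low count on the next regimen can become the participant's worst grade. All-causality AE and SAE tables take in new events in the same way.

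The incidence of AEs and SAEs and laboratory abnormalities are primary endpoints (Protocol Table 4-1). Under Protocol 7.4 the sponsor will review safety in the 12 participants against non-Chinese patients, and a marked difference could lead to a lower dose being studied or more participants being enrolled. The unwanted contribution tends to raise apparent toxicity. In a group of 12, one or two participants can change the impression given by a table row.

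**Working it through.** **1. The plan's own safety figure.** SAP 5 states a 90% probability that 12 subjects show at least one case of an AE with 18% incidence. Check: 1 − 0.82^12 = 0.908. This reproduces, and a cut at subsequent therapy would not change it.

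**2. Is a cut restored elsewhere?** SAP 6.1 has none and shows no redaction. SAP 7.6.1 to 7.6.5 and 7.6.10 add none. Parts of 7.1.1 are redacted, and the Data Presentation Plan named in SAP 9 was not available. On the visible text, nothing restores it.

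**3. How much of the window could fall under a new regimen?** If the new regimen starts S days after the last dose, 100 − S days remain. S is assumed; the documents give no timing.

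| S (days) | Days left in window | Nominal visits after the start |
|---|---|---|
| 14 | 86 | 30, 60, 100 |
| 28 | 72 | 30, 60, 100 |
| 42 | 58 | 60, 100 |
| 60 | 40 | 100 |

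**4. How many extra participants?** Let f be the fraction who start a new therapy within the window, and q the fraction of those who get a new event or grade shift from it that is captured. Both are assumptions. Expected extra participants = 12fq. Chance of at least one = 1 − (1 − fq)^12.

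| f | q | fq | 12fq | Chance of at least one |
|---|---|---|---|---|
| 0.1 | 0.1 | 0.01 | 0.12 | 11% |
| 0.3 | 0.2 | 0.06 | 0.72 | 52% |
| 0.5 | 0.3 | 0.15 | 1.8 | 86% |
| 0.7 | 0.5 | 0.35 | 4.2 | 99% |

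The formula gives all 12 participants the 100-day window. Anyone who received BMS-986205 alone has 30 days, which lowers f.

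**5. What one participant is worth.** 1/12 = 8.3 percentage points in a given table row. Parameters are tabulated separately, so extra participants need not fall in the same row.

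**6. Effect on one rare finding.** For an event with a true 5% rate on study drug (assumed), the chance of at least one in 12 is 1 − 0.95^12 = 0.46. If 4 of the 12 start a new regimen in the window and each has probability 0.3 of the same event from it, the chance becomes 1 − 0.95^12 × 0.7^4 = 0.87.

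**The case against.** **Events are not automatically attributed to the study drugs.** A reader might infer that adverse events of the next regimen are reported as toxicity of BMS-986205 plus nivolumab. The documents do not support that. The general AE tables are declared all-causality, separate drug-related tables exist, and Protocol Appendix 3 tells investigators to weigh concomitant therapy when judging causality. An event attributed to the next regimen stays out of the drug-related tables unless causality is missing. AEs leading to study-drug discontinuation are largely unaffected. This objection stands for AEs. It does not help the laboratory tables.

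**Time off dosing is not contamination.** A participant who stops after two cycles has 56 dosing days and 100 follow-up days, so 100/156 = 64% of that span is off dosing. It is tempting to read this as the contaminated share, but it is not time on a new regimen. Nivolumab exposure also persists: Protocol 9.2.6 equates 5 half-lives plus 30 days with 23 weeks, so one half-life is about (161 − 30)/5 = 26 days. A long window is a reasonable way to catch late immune-mediated events, and collecting data through it is deliberate.

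**Capture is limited.** Only three post-treatment blood draws are scheduled, so a nadir between visits may be missed. A Day 100 visit held on Days 101 to 110 is already outside the window. This lowers q but does not supply a cut; Table 2-4 also allows extra blood counts when clinically indicated.

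**Listings exist and the review is qualitative.** Subsequent therapy, AEs and laboratory values are all listed by participant, and Protocol 7.4 sets no numerical threshold. A careful reader could trace cases by hand, but the summary tables would still mix the two sources. Whether the non-Chinese data use the same uncut window is not stated. If they do, replacing the 100-day tables here would harm the comparison, which is a reason to keep them.

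**Conclusion.** The gap is real and worth closing as a cheap improvement. It matters most for the laboratory worst-grade and shift tables and the hepatic counts, which have no causality filter. It matters next for the all-causality AE and SAE tables of the combination phase. It reaches the drug-related tables only through missing or mistaken causality.

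The size cannot be derived from the documents. The range of about 0.1 to 4.2 expected extra participants rests wholly on the assumed f and q and shows only that the effect could be negligible or substantial. A reader might conclude that the 100-day window is wrong or should be replaced. The documents do not support that either, because the window serves late immune-mediated events. What is missing is a second view that separates data collected after the next therapy began.

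**What to change.** 1. **Keep the 100-day (or 30-day) tables** as planned.
2. **Add supportive tables** in SAP 7.6: laboratory worst grade, laboratory shift, hepatic counts, and all-causality AEs and SAEs. Truncate them at the earlier of 100 (or 30) days after the last dose and the day before the first subsequent anti-cancer therapy.
3. **Define the cut date in SAP 6.1.** Count only therapy started after the last dose of study treatment. Exclude palliative radiotherapy given during a treatment hold, which Protocol 7.7.3.1 permits. The best-overall-response definition should not be reused unchanged, because it includes tumor-directed radiotherapy.
4. **Guard against imputed dates.** SAP Appendix 1 moves partial radiotherapy and surgery start dates early: to the first dose, the first of the month, or the later of 1 January and the first dose. State that, for this cut, an imputed start date may not fall on or before the last study dose.
5. **Flag** AEs and laboratory values after the cut date in the listings.
6. **Interpret both sets side by side**, including in the comparison with non-Chinese patients. Neither should be the sole basis for the laboratory conclusion.

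Cost: SAP wording and a little more programming. The therapy data are already collected, and no extra visits or participants are needed. The downside is that late immune-mediated events arising after new therapy appear only in the 100-day version, so that version must stay.
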